## **5.4. Investigational Product Supplies**

### **5.4.1. Dosage Form(s) and Packaging**

Blinded PF-06649751 and its matched placebo will be provided as tablets for oral administration. The 1 mg, 5 mg, and their matching placebos will be supplied in weekly blister cards. At each dispensing visit, subjects will receive sufficient quantity of investigational product (IP) to last until their next scheduled visit. Each blister card will be labeled according to local regulatory requirements.

### **5.4.2. Preparation and Dispensing**

The PF-06649751 1 mg, 5 mg, and its matched placebo should be dispensed using a drug management system at each visit. A qualified staff member will dispense the investigational product via unique container numbers in the blister provided, in quantities appropriate for the study visit schedule. The subject/caregiver should be instructed to maintain the product in the blister cards provided throughout the course of dosing and return the blister cards to the site at the next study visit.

## **5.5. Administration**

For L-dopa, subjects should be instructed to take the L-dopa in accordance with instructions provided in the product labelling information, at a dose and frequency per the instructions of the investigator and in consideration of the administration instructions provided in the instructions in Section 5.5.1 ([Titration of PF-06649751](#)); Section 5.5.2 ([Period A: Primary Efficacy](#)) and Section 5.5.3 ([Period B: Maintenance](#)).

For PF-06649751 or placebo, subjects (and caregivers, as applicable) should be instructed as follows:

- Take 3 tablets at approximately the same time each morning.
- Swallow each tablet whole, with water.
- Do not manipulate or chew the tablet prior to swallowing.
- All 3 tablets should be taken within approximately 5 minutes.
- The tablets may be taken with or without food.
- If L-Dopa is taken in the morning, the PF-06649751 or placebo tablets may be taken before or after the morning dose of L-Dopa.

- Subjects will document the timing of PF-06649751 or placebo dose on study visit days.

### 5.5.1. Titration of PF-06649751

Each subject is planned to be up-titrated in a double-blind fashion to the assigned target dose level of PF-06649751 or placebo according to the following titration scheme:

**Table 2. Proposed Titration Schemes for PF-06649751 and Placebo Doses**

Week/ Start Day of Dose Level	Treatment Group				
	Placebo	1 mg	3 mg	7 mg	15 mg
Week 1 / from Day 1	P	1 mg	1 mg	1 mg	1 mg
Week 2/ from Day 8	P	1 mg	3 mg	3 mg	3 mg
Week 3 / from Day 15	P	1 mg	3 mg	7 mg	7 mg
Weeks 4-15 / from Day 22	P	1 mg	3 mg	7 mg	15 mg

**Titration (Week 1 to Week 3):** No modifications to the upward titration of Study Medication can be made. Subjects who experience intolerable adverse events during titration will need to be discontinued from the study.

**Post Week 3 (Week 4 to Week 5):** For subjects who experience unacceptable new adverse events after having achieved the target dose (after Day 21) and deemed related to the dose increase, the dose of investigational product can be changed to the previous dose level (Week 3 dose level). This results in a dose reduction from 15 mg/day to 7 mg/day for the highest dose group, and no change in dose for the other dose groups in a blinded fashion. Only one dose modification of investigational product is permitted.

**L-Dopa Adjustment for Unacceptable Dopaminergic Side Effects (Week 1 to Week 15):** In the case of unacceptable dopaminergic side effects and following discussion with the Medical Monitor, the dose of L-Dopa may be reduced between Day 1 and Day 105 visit.

### 5.5.2. Period A: Primary Efficacy

During Period A, subjects will be administered double blind study medication once daily (up to 4 different dose levels of investigational product) as adjunctive treatment to a stable dose of open-label L-Dopa.

### 5.5.3. Period B: Maintenance

After the Week 10 Visit (primary endpoint collection), subjects will enter Period B. During Period B, double-blind treatment with investigational product will continue as adjunctive treatment to a stable dose of open label L-Dopa.

## **5.6. Investigational Product Storage**

The investigator, or an approved representative, eg, pharmacist, will ensure that all investigational products are stored in a secured area with controlled access under required storage conditions and in accordance with applicable regulatory requirements. An Investigational Product Manual will be supplied to the pharmacy prior to initiation of the study and will provide further information regarding storage conditions of the product.

Investigational product should be stored in its original container and in accordance with the label. Site staff will instruct subjects on the proper storage requirements for taking home investigational products, including how to report temperature excursions. See the single reference safety document (SRSD) for this study, the Investigator's Brochure for PF-06649751.

Storage conditions stated in the Investigator's Brochure will be superseded by the storage conditions stated in the labeling.

Site systems must be capable of measuring and documenting (for example, via a log), at a minimum, daily minimum and maximum temperatures for all site storage locations (as applicable, including frozen, refrigerated and/or room temperature products). This should be captured from the time of investigational product receipt throughout the study. Even for continuous monitoring systems, a log or site procedure that ensures active daily evaluation for excursions should be available. The operation of the temperature monitoring device and storage unit (for example, refrigerator), as applicable, should be regularly inspected to ensure it is maintained in working order.

Any excursions from the product label storage conditions should be reported upon discovery. The site should actively pursue options for returning the product to the storage conditions as described in the labeling, as soon as possible. Deviations from the storage requirements, including any actions taken, must be documented and reported to the sponsor. Once an excursion is identified, the investigational product must be quarantined and not used until the sponsor provides documentation of permission to use the investigational product. It will not be considered a protocol deviation if the sponsor approves the use of the investigational product after the temperature excursion. Use of the investigational product prior to sponsor approval will be considered a protocol deviation.

Specific details regarding information the site should report for each excursion will be provided to the site.

## **5.7. Investigational Product Accountability**

The investigative site must maintain adequate records documenting the receipt, use, loss, or other disposition of the investigational product supplies. Subjects will return Investigational Product to the site per the [Schedule of Activities](#). Additional details regarding the process for accountability will be provided prior to initiation of the study.

### **5.7.1. Destruction of Investigational Product Supplies**

The sponsor or designee will provide guidance on the destruction of unused investigational product (eg, at the site). If destruction is authorized to take place at the study site, the investigator must ensure that the materials are destroyed in compliance with applicable environmental regulations, institutional policy, and any special instructions provided by Pfizer, and all destruction must be adequately documented.

### **5.8. Concomitant Treatment(s)**

Subjects will abstain from all concomitant medications as outlined in [Appendix 3](#) and [Appendix 4](#) except for:

- The treatment of adverse events.
- [Rescue Medication](#), as described in Section 5.9.
- All concomitant medications taken during the study must be recorded with indication, daily dose, and start and stop dates of administration. All subjects will be questioned about concomitant medication at each clinic and telephone visit.

Medications taken within 60 days before the first dose of study investigational product will be documented as a prior medication. Medications taken after the first dose of study investigational product will be documented as concomitant medications.

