Based on the observed exposures from the 15 mg cohort in study B7601005, the top dose of 15 mg QD dose is expected to provide exposure ~2-3 fold lower than the stopping criteria from 15 week monkey toxicological study. Given the CYP3A4 mediated metabolism of PF-06649751, this provides a margin to allow for a possible increase in exposure of PF-06649751 when used together with weak inhibitors of CYP3A4. Patients receiving moderate to strong CYP3A4 inhibitors will be excluded from the study until further elucidation of the exact interaction magnitude in a drug-drug interaction study.

Therefore, based on the objectives to identify a minimum efficacious dose, maximum efficacious dose and evaluate dose-response, the following four PF-06649751 doses are proposed for the study along with a placebo: 1 mg QD, 3 mg QD, 7 mg QD and 15 mg QD PF-06649751.

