### **5.8.2. Prohibited Other Concomitant Medications**

The following medications will not be permitted within 28 days prior to Randomization:

- CYP3A4 inducers: the use of moderate and strong inducers of CYP3A4 is not permitted, since they may decrease the levels of PF-06649751. A list of potential drug inducers is provided in [Appendix 4](#).
- CYP3A4 inhibitors: the use of moderate or strong inhibitors of CYP3A4 is not permitted throughout the study since concomitant use these may lead to increased levels of PF-06649751. A list of potential CYP3A4 inhibitors is provided in [Appendix 4](#).
- The use of marijuana is not permitted from Screening through the end of the double blind treatment period.

The following medications will not be permitted within 42 days prior to Randomization:

- The use of amphetamines, methylphenidate or other stimulants.
- Antipsychotics (except stable low dose quetiapine), metoclopramide, or reserpine are not permitted.
- Lithium, MAO-A/B inhibitor antidepressants (including moclobemide, tranylecypromine, and phenelzine); stable low dose opioids for chronic painful medical conditions may be permitted based on a consultation with the medical monitor.
- Antiepileptics are not permitted except if used for chronic painful conditions at steady doses (for example, gabapentin or pregabalin).

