### Appendix 3. Permitted/Prohibited Concomitant Medications

Use Category	Type of Medication	Guidance
Permitted	Any previous, current or new medications for medical illness not listed under the prohibited medication section below.	As needed based on investigator's judgment and subject's medical needs 
	Hypnotics, sedatives, anxiolytics	Stable low doses of benzodiazepines are permitted. The planned prescription of benzodiazepines for P.r.n. ("as needed") use throughout the study should be discussed with the medical monitor/Pfizer Clinician. For insomnia, non-benzodiazepine hypnotics are permitted.
	Monoaminoxidase B (MAO-B) inhibitors	Permitted if at a stable dose for at least 42 days prior to Randomization. No dose changes should be anticipated for the duration of the study.
	Catechol O methyltransferase (COMT) inhibitors	Permitted if at a stable dose for at least 42 days prior to Randomization.
	Antidepressants except MAO-A/B inhibitor antidepressants	Permitted if subject is taking a stable dose at least 42 days prior to Randomization.
	Anticholinergics	Permitted if at a stable dose for at least 42 days prior to Randomization. No dose changes should be anticipated for the duration of the study.
	Amantadine	Permitted if at a stable dose for at least 42 days prior to Randomization. No dose changes should be anticipated for the duration of the study.
Prohibited	Dopamine receptor agonist medications including pramipexole, ropinirole, rotigotine and apomorphine	Prohibited for at least 28 days prior to Randomization and through the end of the double blind treatment period.
	Istradefylline and zonisamide	Prohibited for at least 42 days prior to Randomization and through the end of the double blind treatment period.
	Inhaled L-Dopa, intraduodenal use of Duodopa®	Not permitted.
	Antipsychotics or neuroleptics	Antipsychotics (except stable low dose quetiapine), metoclopramide, or reserpine are not permitted.
	Antiepileptics	Antiepileptics are prohibited except if used for chronic painful conditions at steady doses (for example, gabapentin or pregabalin).
	Lithium, MAO-A/B inhibitor antidepressants (including moclobemide, tranylcypromine, and phenelzine)	Prohibited for at least 42 days prior to Randomization and throughout the study. Stable low dose opioids for chronic painful medical conditions may be permitted based on a consultation with the medical monitor.

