	Moderate or Strong CYP3A Inhibitors and Inducers	Drugs that induce or inhibit the hepatic metabolizing cytochrome 3A4 enzymes; CYP3A inducers or inhibitors are prohibited from at least 28 days prior to Randomization
	Marijuana	Prohibited from Screening through the end of the double blind treatment period.

1. Investigator to discuss with sponsor as needed.

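### Section 5.8 exempts adverse-event treatment from the prohibited-medication lists without limiting drug class, which contradicts the CYP3A inhibitor ban elsewhere in the protocol (minor)

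*Protocol*

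**What the plan says.** Protocol Section 5.8 begins: "Subjects will abstain from all concomitant medications as outlined in [Appendix 3](#) and [Appendix 4](#) except for". The first listed exception is "The treatment of adverse events". It names no excluded drug class, asks for no consultation and says nothing about investigational product.

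Other parts of the protocol deal with the same drugs:

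- Section 5.8.2: "the use of moderate or strong inhibitors of CYP3A4 is not permitted throughout the study", because plasma levels of study drug may rise.
- Appendix 3, prohibited section: "CYP3A inducers or inhibitors are prohibited from at least 28 days prior to Randomization".
- Appendix 3, first Permitted row: "Any previous, current or new medications for medical illness not listed under the prohibited medication section below". Its footnote adds "Investigator to discuss with sponsor as needed".
- Section 4.4.1: grapefruit, which Appendix 4 lists as an inhibitor, is barred from 7 days before the first dose until double-blind medication ends.
- Section 1.5.2: exposure at 15 mg "is expected to provide exposure ~2-3 fold lower than the stopping criteria from 15 week monkey toxicological study", and "this provides a margin to allow for a possible increase in exposure of PF-06649751 when used together with weak inhibitors of CYP3A4". Patients on stronger inhibitors are kept out until a drug-drug interaction study has been done.
- Exclusion criterion 17: the same inhibitors and inducers exclude a patient, with topical use exempt.

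**The concern.** The exception in 5.8 attaches to a sentence that names Appendix 4, and that appendix contains nothing but moderate or strong CYP3A inhibitors and inducers. The exception therefore reaches exactly the drugs that 5.8.2 bars. The situation is an ordinary one. Appendix 4 includes clarithromycin, ciprofloxacin, fluconazole and aprepitant; an intercurrent infection is an adverse event; and Section 1.4.2 names nausea and emesis as adverse drug reactions of the study drug. A site could prescribe one of these, cite 5.8, and leave the subject on 15 mg.

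What is at stake is the condition on which the 15 mg dose was justified. Metabolism is CYP3A4-mediated, the stated margin is offered for weak inhibitors, and the size of a stronger interaction is treated as unknown. Apart from general provisions for unplanned visits (6.5) and withdrawal for safety (6.6), no rule tells a site what to do with investigational product if such a drug is unavoidable.

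**Working it through.** **The texts side by side.**

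| Place | Systemic moderate or strong CYP3A inhibitor, given on study for an adverse event |
|---|---|
| 5.8, first exception | Allowed on a literal reading |
| 5.8.2, inhibitor bullet | Not allowed |
| Appendix 3, prohibited CYP3A row | Not allowed; start date given, no end date |
| Appendix 3, first Permitted row | Not allowed, because the drug is on the prohibited list |
| 4.4.1 | Even grapefruit is barred on study |
| 1.5.2 | Outside what the margin is meant to cover |

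Could the exception be read as covering only harmless drugs? It would then do nothing, because the first Permitted row of Appendix 3 already allows new drugs that are not prohibited. As applied to Appendix 4, it can release only inhibitors or inducers.

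How firmly is the on-study ban stated? The sentence that introduces the inhibitor bullet in 5.8.2 refers to the 28 days before randomization, and the Appendix 3 row gives no end. The on-study ban therefore rests mainly on the closing words of the 5.8.2 inhibitor bullet, supported by 4.4.1.

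**The plan's own margins, reproduced.** Inputs are the unbound exposures in Section 1.3.3. Human at 15 mg: Cmax 19.8 ng/mL, AUC 366 ng·h/mL. Monkey 39-week NOAEL (no-observed-adverse-effect level): 79.5 and 818. Male rat 26-week NOAEL: 113 and 770. Margin = NOAEL exposure / human exposure.

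- Monkey: Cmax 79.5/19.8 = 4.02; AUC 818/366 = 2.23.
- Rat: Cmax 113/19.8 = 5.71; AUC 770/366 = 2.10.

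These match the stated 4x, 2.2x, 5.7x and 2.1x. The 2 to 3 fold figure in 1.5.2 cannot be recomputed, because the stopping limit is not given.

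**What an interaction would do to the 1.5.2 margin.** The documents give no interaction size, so the multiplier m is an assumption shown over a range. Exposure as a share of the stopping criteria runs from m/3 to m/2.

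| Assumed m | Share of stopping criteria |
|---|---|
| 1.5 | 50% to 75% |
| 2 | 67% to 100% |
| 3 | 100% to 150% |
| 5 | 167% to 250% |

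The stated margin is used up at m between 2 and 3.

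**Who could be concerned.** Planned 15 mg subjects: 54 × 2/3 + 144 × 1/8 = 36 + 18 = 54 of 198 (27%). How many would need such an inhibitor is not known and is probably few.

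**The case against.** The best defence is that specific text governs general text. Section 5.8.2 is the specific provision and gives its reason, Appendix 3 agrees, and a protocol that bars grapefruit on study plainly does not mean to allow clarithromycin. The list in 5.8 is also loosely drafted: its third item is an instruction to record medications, not an exception, so a strictly literal reading of the list does not parse. The first item may be no more than ordinary latitude for necessary care. Nor would such a subject go unwatched. Concomitant medication is asked about at every clinic and telephone visit, unplanned visits include triplicate ECG and vital signs, either side can withdraw a subject for safety, and an external committee reviews unblinded safety data. Section 1.5.2 is mainly eligibility language, so it conflicts in rationale more than as an on-study rule.

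Most of this stands, and it is why the point is minor. It does not remove the contradiction, which sits in the lead-in of the governing section. The Appendix 3 footnote on discussion with the sponsor is attached to the Permitted row, so it is not a safeguard for a prohibited drug. None of the monitoring provisions says what to do with investigational product.

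A reader might infer two stronger things. One is that the protocol intends to let 15 mg subjects take these inhibitors; the specific passages show that it does not. The other is that such subjects would reach toxic exposure. The documents do not support that either. The interaction size is absent, the rat vascular finding did not appear in studies up to 15 weeks, the monkey NOAEL was the highest dose tested, and the Cmax margins are wider than the AUC margins. The spread of exposure at 15 mg comes from only 7 subjects (Table 1), too few to carry an estimate of how many would cross a limit.

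**Conclusion.** The inconsistency is real and minor. An operative sentence in 5.8, followed as written, allows what 5.8.2, Appendix 3 and 4.4.1 forbid and what the 15 mg rationale in 1.5.2 does not cover. The textual conclusion needs no numerical assumption. The statement that the margin is used up at 2x to 3x takes the protocol's own 2 to 3 fold figure at face value and says nothing about how large the interaction would be. The primary analysis is not affected: the Full Analysis Set in SAP Section 4.1 classifies subjects by randomized arm whatever they take alongside, and few cases are expected.

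**What to change.** Amend the first bullet of 5.8 so that the exception covers adverse-event treatment only with medications not prohibited by Sections 5.8.1 and 5.8.2 or Appendices 3 and 4, with topical use allowed as in exclusion criterion 17. Add that if a systemic prohibited medication is medically essential, in particular a moderate or strong CYP3A inhibitor, the site contacts the Medical Monitor before or when it is started. They then decide whether investigational product is continued, interrupted or stopped. Naming Appendix 4 in the bullet avoids relying on the 28-day lead-in of 5.8.2. A clarification letter to sites can cover the time until the next amendment.

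The cost is slightly less site latitude in treating adverse events. Sample size, power and error rates do not change.

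A mandatory hold with re-titration is not recommended. Sites are blinded, so it would apply in every arm, although 144 of 198 planned subjects are not on 15 mg (36 of them on placebo). For a 15 mg subject, a 7-day course followed by the 3-week Table 2 titration would take 7 + 21 = 28 of the 35 days of Period A below target dose. A case-by-case decision protects the subject without that loss in every case.

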#### **5.8.1. Medications for Parkinson's disease**

Permitted Parkinson's disease medications:

- Subjects must be on a stable dose of L-Dopa of at least 400 mg total daily dose for at least 21 days prior to Randomization, in conjunction with a dopa-decarboxylase inhibitor (eg, L-Dopa/carbidopa or L-Dopa/benserazide) divided into at least 4 doses per day. Subjects on a stable dose of L-Dopa of at least 400 mg/day divided into 3 daily doses (TID) may be considered and authorized on a case-by-case basis if submitted as part of the screening assessment to the sponsor and/or its designee for determination if the dosing regimen is considered optimized for that particular subject.
- MAO-B inhibitors or COMT inhibitors, amantadine, and anticholinergics are permitted but should remain at stable dose from 42 days prior to Day 0 (Randomization) through the end of the double blind treatment period.

Prohibited Parkinson's disease medications:

- Dopamine receptor agonist medications including pramipexole, ropinirole, rotigotine and apomorphine are prohibited for at least 28 days prior to Randomization and through the end of the double blind treatment period.

- Istradefylline and zonisamide are prohibited 42 days prior to Randomization and through the end of the double blind treatment period.
- The use of inhaled L-Dopa is prohibited from Screening through the end of the double blind treatment period.
- Subjects with prior implantation of apomorphine pump, or surgery for intraduodenal use of Duodopa® are not eligible.

### **5.8.2. Prohibited Other Concomitant Medications**

The following medications will not be permitted within 28 days prior to Randomization:

- CYP3A4 inducers: the use of moderate and strong inducers of CYP3A4 is not permitted, since they may decrease the levels of PF-06649751. A list of potential drug inducers is provided in [Appendix 4](#).
- CYP3A4 inhibitors: the use of moderate or strong inhibitors of CYP3A4 is not permitted throughout the study since concomitant use these may lead to increased levels of PF-06649751. A list of potential CYP3A4 inhibitors is provided in [Appendix 4](#).
- The use of marijuana is not permitted from Screening through the end of the double blind treatment period.

The following medications will not be permitted within 42 days prior to Randomization:

- The use of amphetamines, methylphenidate or other stimulants.
- Antipsychotics (except stable low dose quetiapine), metoclopramide, or reserpine are not permitted.
- Lithium, MAO-A/B inhibitor antidepressants (including moclobemide, tranylecypromine, and phenelzine); stable low dose opioids for chronic painful medical conditions may be permitted based on a consultation with the medical monitor.
- Antiepileptics are not permitted except if used for chronic painful conditions at steady doses (for example, gabapentin or pregabalin).

